Two possible developments are high-intensity interval training (HIIT) and home-based supported exercise programmes (HEP). One previous study in the USA using a HIIT programme demonstrated that patients in the HIIT group had similar improvements in peak oxygen uptake (VO_{2Peak}), PFWD and MWD compared to those who completed low-intensity exercise (12). However, high-intensity was prescribed using 80% of the maximum workload (i.e. treadmill grade) achieved during the initial baseline maximal effort test (12), which is slightly conservative, given that HIIT is usually prescribed between 85-95% of peak workload or HR (15, 16). Despite this limitation, this study does suggest that HIIT may be at least as effective as current exercise programmes and should be explored as an alternative SEP treatment option.

In comparison to HIIT there has been much more evidence for the use of HEP. One randomised controlled trial (RCT) in the USA demonstrated that HEP significantly improved PFWD and MWD with results equivalent to the SEP (17). With increasing technologies HEPs or "facilitated self-managed exercise programmes" are becoming more prominent. Indeed, a study identifying patient preference in the IC literature demonstrated that over half of patients would prefer to exercise in the home setting (Harwood et al, JVN 2018).

Study Aims:

This study aims to compare the efficacy and acceptability of two novel exercise interventions (HIIT and HEP) versus current practice (SEP) for exercise rehabilitation in IC. As a cycle-based HIIT protocol has not been previously investigated in the IC population an initial observational cohort study of HIIT will be conducted, followed by semi-structured interviews, meaning the research will be split into two work-streams.

Work-stream 1: Considering the safety, tolerability, acceptability and efficacy of high-intensity interval training as a novel intervention for the treatment of intermittent claudication.

Study-design: A Two-centre, mixed methods, prospective, “proof of concept” cohort study.

Objective: To investigate the utility, safety, tolerability, acceptability and efficacy of high-intensity interval training as a novel intervention for the treatment of intermittent claudication.

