Primary outcomes measures: Utility, assessed by screening, eligibility, recruitment and adherence rates. Safety, assessed by determining the occurrence of adverse and serious adverse events, and tolerability, assessed by patient ability to achieve and maintain exercise in the appropriate exercise intensity domain.

Secondary outcome measures: Acceptability assessed via semi-structured interview and changes in MWD and PFWD assessed via graded treadmill test, VO_{2Peak} , ventilatory anaerobic threshold (VAT) assessed via CPET, ABPI and QoL.

Primary endpoint

The primary endpoint for this study will be assessing the utility, safety and tolerability of a 6-week HIIT intervention.

Secondary endpoints

Additional endpoints will include acceptability and improvements in MWD, PFWD, VO_{2Peak} , VAT, ABPI and QoL.

Study design**Identification and screening of patients:**

Potential participants will be identified by vascular surgeons / nurses / technologists (as appropriate to each site) in vascular outpatient clinics or multidisciplinary team meetings (as appropriate to each site) at two tertiary vascular centres, Hull Royal Infirmary (Hull, United Kingdom) and University Hospital Coventry and Warwickshire (Coventry, United Kingdom)

and referred to research nurses / research fellows or exercise physiologists (appropriate to each site) for screening..

Patient Selection

Patients will have a confirmed diagnosis of intermittent claudication made by their consultant either clinically or by questionnaire. Diagnosis will be made with an ABPI of <0.9, a drop-in ankle pressure of ≥ 20 mmHg after exercise, or documented significant atherosclerosis on radiological imaging.

Patient consent

Patients will be sent a letter and patient information sheet. This will provide details of the study, the 6-week HIIT programme and the interview. Patients will then be contacted via telephone call at least a week later to ask any questions and decide whether they would like to partake in the study intervention. Those who do not wish to partake in the research will be offered the usual care SEP without research as is usual practice for IC. Those who also decline this will be referred back to their consultant for future management.

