This study will utilise a cycle CPET with a ramp protocol at each study visit as a non-invasive assessment of cardiovascular function, utilising a safety protocol on the basis of the ACSM guidelines (19). Prior to the start of the test the patient will observe a 3-minute rest period whilst sitting on the cycle ergometer so that resting measurements can be obtained. After this, the patient will begin a 3-minute reference or warm-up period of unloaded cycling followed by progressive graded exercise with adequately increasing workload to induce volitional exhaustion within 8-12 minutes, concluding with a post-maximal effort recovery period (26). During the CPET, patients will be continuously monitored via a 12-lead electrocardiogram (ECG; applied after adequate skin preparation), with measurements of HR, blood pressure and rating of perceived exertion (RPE) taken at regular intervals (19). Patients will also be observed for any signs or symptoms and asked to confirm that they are asymptomatic periodically throughout (19). Upon completion of the CPET, this monitoring will continue for at least 6 minutes or until ECG changes return to baseline and significant signs and symptoms subside (19, 27). HR and blood pressure will also be monitored until they return to near resting values (19). Gas analysis will also be conducted on a breath-by-breath basis to allow determination of important secondary outcome measures such as VO_{2Peak} and VAT. VO_{2Peak} will be determined as the average oxygen uptake value during the last 30-seconds of the test whilst VAT will be estimated using the widely adopted V-slope method and verified using the ventilatory equivalents (28).

Spirometry, which will be performed prior to CPET, is an effective screening tool of general respiratory health that can be used to establish whether exercise intolerance is primarily

caused by or contributed to by ventilatory limitation (29, 30). Therefore, unforced (vital capacity; VC and inspiratory capacity; IC) and forced (forced expiratory volume in 1 second; FEV₁ and forced vital capacity, FVC) spirometry manoeuvres will be conducted, in line with American thoracic society guidelines, to substantiate the extent of any respiratory limitation during CPET (29, 30).

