The study requirements and participant expectations will be clearly explained in the patient information sheet. This will be sent to the patient and they will be given adequate time to read it at their own leisure without any pressure to partake in the study from the researcher. Informed consent will only be obtained once patients have understood all study requirements, asked any questions they may have and have agreed to participate.

Patients will be required to attend their exercise sessions 3 times per week for 6 weeks. This may be problematic for patients and may cause them to decline this intervention or withdraw once recruited. However, this may also provide a patient benefit, as this means the patient only has to attend half the number of sessions than is usually required for SEP. Furthermore, travel and parking costs may prove to be a barrier. Travel expenses for study visits (baseline and follow-ups) will be reimbursed. Patients can be reimbursed a maximum of £75 to cover the costs of transport/parking that may be accrued.

Patients will be required to attend three or four 2-3-hour study visits. This time, on top of the time required to undertake the intervention may preclude some patients from taking part in the study.

Some study elements (such as CPET or HIIT) may propose a risk to the participants. HIIT is a novel intervention in the IC population, meaning its safety is unknown. However, a large multi-centre RCT in the cardiac population (similar disease aetiology to IC) demonstrated that HIIT was a safe intervention (15). Furthermore, standards for exercise testing from the American heart association, note that the occurrence of death as a result of testing is rare with a frequency estimated at 1 per 10000 tests, maybe less (26). Therefore, although the testing and intervention procedures carry some risk, it is minimal and is outweighed by the potential patient benefits.

Sample size

Due to the pilot nature of this proof of concept study it is not possible to calculate the sample size. The main aim is to assess the conceptual benefit of the proposed interventions. We aim to recruit 20 patients from the additional Coventry site, which in addition to the target of 50 patients at the Hull site, totals 70 patients.

Descriptive statistics and statistical analysis

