Data obtained from all participants will be included in the data analysis and no data will be excluded on the basis of intervention and follow-up adherence. Therefore, all collected data at each time point will be analysed.

Baseline characteristics will be summarised descriptively using mean (\pm SD) for normally

distributed data and using median and range for non-normally distributed data. Categorical variables will be presented as frequency and percentages.

Rates of uptake, completion, dropout, adverse or serious adverse events and missing outcome data will be summarised and participation in the intervention will be described as the mean number of sessions attended and the mean time to completion (in weeks) to allow for comparison between actual and theoretical total intervention time.

In addition, tolerability will be assessed by comparing the mean heart rate achieved during each HIIT session to the 85-100% maximum heart rate range calculated from CPET.

Secondary endpoints such as changes in MWD, PFWD, VO_{2Peak} , VAT, ABPI and QoL at each time-point will be assessed using a repeated-measures general linear model.

All quantitative analyses will be conducted using the SPSS statistics software at the conventional two-sided 5% significance level with results presented as mean difference with 95% confidence intervals, associated *p* values and effect sizes where appropriate. Sub-group analysis will also be conducted comparing those who are able to give maximal effort during baseline CPET (and therefore able to perform maximal HIIT) and those who are not (therefore performing submaximal HIIT). Maximal effort will be based on previously published criteria (19, 38). Further sub-group analysis will also be performed comparing those who satisfactorily completed the intervention (i.e. completed $\geq 15/18$ sessions) and those who did not, presuming they do not withdraw from the intervention.

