<https://www.hra.nhs.uk/approvals-amendments/managing-your-approval/progress-reports/> will be used. It will be completed and signed by the chief investigator and emailed to the REC within 30 days of the anniversary date of the favourable opinion and annually until the trial is completed.

Data collection, handling, management and record keeping

Data will be collected by the local principal investigator at all time points during the study. Collection of data will be via standardised questionnaires (VascuQoL and SF-36) and physical assessment. To ensure completeness of data, questionnaires will be issued and completed during the study visits to allow patients to ask questions or clarify information about the questionnaire. Data will be collected and retained in accordance with the Data Protection

Act 1998. All patients will be given a study code along with the abbreviate hospital title to ensure anonymity, for example the first patient recruited at Hull and Coventry would be 01H and 01C respectively. Data will be stored on computers in the research office at the vascular laboratory in Hull Royal Infirmary and Coventry and Warwickshire University Hospital respectively with the same identification code. These computers are password protected and have both antivirus and firewall software. Only named investigators will have access to the patient data. Transfer of electronic data will be anonymous and only be carried out through encrypted password protected USB devices or via the secure www.nhs.net email account. Data will be stored for five years following trial completion.

IT services department has a backup procedure approved by auditors for disaster recovery. Servers are backed up to disk media each night which run on a 4-week cycle, meaning anything deleted more than 4 weeks previously is lost. Files remain on the server unless deleted either accidentally or deliberately. Additional 'archive' backups are taken for archived data, so data should not be lost from this system e.g. FileVision. Disks are stored in a fireproof safe.

Study documents (paper and electronic) will be retained in a secure location during and after the trial has finished. All essential documents including source data will be retained for a minimum period of 5 years after study completion. A sticker stating the date that documents need to be retained until will be placed on the inside front cover of participant case report forms.

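### The plan does not say who reads the ventilatory threshold or mask the visit; in a one-group before-after study, masked random-order reading is a cheap safeguard

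*Combined protocol and SAP*

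**What the plan says.** All references are to the combined protocol and SAP.

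- **How VAT is obtained.** Under Cardiorespiratory measures, CPET/spirometry: "VAT will be estimated using the widely adopted V-slope method and verified using the ventilatory equivalents". The same sentence gives VO2Peak a mechanical rule, the mean uptake over the final 30 seconds. For VAT it names no reader, no masking, no second reader and no rule for when the two methods disagree.
- **Who collects data.** Under Data collection, handling, management and record keeping: "Data will be collected by the local principal investigator at all time points during the study".
- **Design.** Study Aims says that "an initial observational cohort study of HIIT will be conducted", and work-stream 1 is described as "Two-centre, mixed methods, prospective". It has one group and no comparator.
- **Status and analysis of VAT.** Under Secondary endpoints: "Additional endpoints will include acceptability and improvements in MWD, PFWD, VO_{2Peak} , VAT, ABPI and QoL". Under Descriptive statistics and statistical analysis, changes in the secondary endpoints "at each time-point will be assessed using a repeated-measures general linear model", at the "conventional two-sided 5% significance level".
- **Size.** The Sample size section adds 20 patients at Coventry, which "in addition to the target of 50 patients at the Hull site, totals 70 patients". It gives no SD, effect size or power for any outcome.
- **Software.** The Study equipment list includes CPET software. The plan does not say whether that software determines VAT.

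**The concern.** VO2Peak follows from a fixed calculation. VAT, as written, is estimated by one method and checked against another, with nothing said about how the two are reconciled. That leaves discretion to whoever makes the reading, and nothing in the plan keeps that person from knowing whether the file is a baseline or a post-training test.

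Random reading error would only add noise. The risk is a directional difference, with thresholds placed slightly higher on average after training. In a randomised comparison, a drift between visits that was equal in both arms would cancel. With one group it does not cancel, and the whole of it is reported as change after HIIT. Efficacy is part of the work-stream objective, so an inflated VAT gain would bear on a stated purpose, although not on the primary outcomes of utility, safety and tolerability.

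**Working it through.** **1. The plan's own figure.** 50 (Hull) + 20 (Coventry) = 70, as stated. There is no power calculation and no VAT figure to reproduce.

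**2. Inputs for the illustration.**
- From the documents: two-sided alpha 0.05; n = 70. This is the recruitment target, so it is the upper limit for patients with paired VAT readings.
- Assumed, not in the documents: SD of within-patient change in VAT of 1.0, 1.5 or 2.0 mL/kg/min; a pure reading shift of 0.1, 0.25 or 0.5 mL/kg/min; no true change.
- Simplification: one paired baseline-to-follow-up contrast stands in for the repeated-measures model.

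**3. Formula.** z = shift / (SD/√n), with √70 = 8.367. The chance of a significant result is Φ(z − 1.96) + Φ(−z − 1.96).

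Worked example: shift 0.25, SD 2.0. z = 0.25 × 8.367 / 2.0 = 1.05. The chance is Φ(−0.91) + Φ(−3.01) ≈ 0.18.

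| Shift (mL/kg/min) | SD 1.0 | SD 1.5 | SD 2.0 |
|---|---|---|---|
| 0.1 | z 0.84, 13% | z 0.56, 9% | z 0.42, 7% |
| 0.25 | z 2.09, 55% | z 1.39, 29% | z 1.05, 18% |
| 0.5 | z 4.18, 99% | z 2.79, 80% | z 2.09, 55% |

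**4. Check with the t distribution.** In units of the SD of change, shifts of 0.1, 0.25 and 0.5 at n = 70 give 13.1%, 54.1% and 98.5% from the noncentral t. These match the SD 1.0 column to within about one percentage point.

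**5. The same point without assuming an SD.** The smallest observed mean change that reaches p < 0.05 is t(0.975, n − 1)/√n, in SD units of change: 0.24 at n = 70, 0.28 at n = 50 and 0.47 at n = 20. A pure reading shift of 0.2 SD gives a significant result in 38%, 28% and 14% of studies respectively.

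**6. Fewer paired readings.** If 50 patients had paired VAT (an assumption), √50 = 7.071. At SD 2.0, a shift of 0.5 gives z = 1.77 and about 42%, against 55% at n = 70. A shift of 0.25 gives z = 0.88 and about 14%, against 18%.

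**7. Is VAT needed at the visit?** The HIIT programme section sets intensity from peak power output and maximum heart rate. The Additional exclusion criteria concern ischaemia or haemodynamic compromise on CPET. The Source data section asks for relevant results, with CPET as an example, in the notes after each visit. None of these names VAT, so the analysed reading can be made later while the safety review and note entries stay where they are.

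**The case against.** A reader might infer that VAT is read by eye, by the principal investigator who ran the test, and that this reader's expectation would by itself produce a significant training effect. The documents support none of these three steps.

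- **Reading by eye.** The text does not say so, and CPET software is listed. Detection could be automated, visual or mixed. What stands is that the method is unstated and the verification step has no rule for disagreement.
- **The reader.** The plan says who collects the data, not who interprets the plots. What stands is that no masking is described for whoever does.
- **The effect.** Both the shift and the SD are assumed. At a shift of 0.1 mL/kg/min the false-positive rate is 13% to 7%, not far from nominal. Patients who stop the programme early are withdrawn, CPET findings can exclude others, and missing values are not imputed, so fewer than 70 pairs are likely and the percentages would be lower.

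Two further objections concern importance, and both are fair. First, VAT is one of several secondary endpoints in a proof-of-concept cohort, no progression rule depends on it, and results are to be given as mean differences with confidence intervals as well as p values. However, a reading shift would move the mean difference and its interval too. Second, masking VAT leaves test familiarisation and regression to the mean in place, and walking distances and Doppler ABPI are also measured by staff who can know the visit. These points limit the value of the change, but they do not justify leaving the VAT reading unspecified.

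**Conclusion.** The point holds as a cheap improvement, not as a flaw that undermines the study. The plan leaves open who or what determines VAT and does not mask the visit, and the one-group design passes any directional reading shift straight into the reported change. The calculation shows only how sensitive the test is: shifts of 0.1 to 0.5 mL/kg/min would give significant results in roughly 7% to 99% of studies, depending on an SD the documents do not supply and on all 70 patients contributing pairs. It is not an estimate of bias in this study. The primary outcomes are unaffected.

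**What to change.** Add to the CPET/spirometry section that the VAT value used in the analysis is read by existing site staff from exported CPET files with patient, visit and date removed, in random order, after the patient's last visit. Preferably the two sites swap files, so that the reader did not run the test; without the swap, masking may be only partial. CPET safety review and entries in the notes stay at the visit. If VAT is in fact determined by software, say so in the same place. In either case, state what happens when V-slope and the ventilatory equivalents disagree.

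**Cost.** File export, coding and batch reading; no extra test or patient visit. With CPET at every visit, the maximum is 50 × 4 files from Hull (baseline and three follow-ups) plus 20 × 3 from Coventry (baseline and two follow-ups), which is 200 + 60 = 260. A swap would move most of the reading to Coventry, which would take 200 files instead of 60, so the sites should agree the split. The data-handling section already provides for anonymous transfer by encrypted device or secure email.

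**Limit.** This removes reading bias in one secondary endpoint. The report should still describe the VAT change as uncontrolled.

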Safety will be determined by the occurrence of any adverse events (AE) or serious adverse events (SAE). In accordance with the GCP decision tree for adverse event reporting all events will be reported to the sponsor and recorded to determine the safety of the intervention.

Utility will include eligibility (n = eligible/screened), recruitment (recruited/eligible), and adherence (number of patients completing the HIIT programme). The number of patients screened, recruited and commencing the HIIT programmes will be monitored at each hospital site. A register (if required, i.e. more than one patient attending), will be taken at each exercise class to record patient adherence and the completeness of each session will be recorded (i.e. how many minutes the patient completed). It is estimated that all patients should complete 18 sessions in total within 6 weeks. However, where any sessions are missed, the intervention period can be extended to 8 weeks to allow these sessions to be added on. Those not completing 18 sessions over the extended 8-week period will be deemed to have satisfactorily completed the intervention as long as they have completed >80% of the intervention (i.e. ≥ 15 out of 18 sessions). All patients completing the allotted 6-8 weeks for the intervention (regardless of whether they have completed \geq or < 15 sessions) will still be followed up. Those choosing to discontinue the intervention before completing the full intervention timeframe will be withdrawn.

Tolerability will be assessed by identifying if patients are able to reach and maintain the prescribed training range required to perform HIIT, for each full interval. Heart rate (HR) data will be collected throughout each HIIT session and saved on an encrypted USB stick this will then be compared to the 85-100%HRMax training range that has been prescribed – to determine if patients are able to achieve it. This range will be in line with an ongoing HIIT trial in CAD at 85-90% peak power output (PPO), aiming to achieve >85%HRMax, derived from CPET (15). If patients are not able to achieve 85-100%, this will determine the suitability of this HIIT protocol in this population. Reasons for stopping the HIIT exercise sessions (e.g. leg pain), will be recorded.

Secondary endpoints

Acceptability

Acceptability will be assessed by patient feedback using semi-structured interviews.

conducted using a sample of patients in three groups:

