This study will use a pragmatic and flexible HIIT protocol with a higher intensity than that previously used in the IC population (12). The protocol will consist of 3 sessions per week for 6 weeks, with a work to rest ratio of 1:1 (one-minute interval of HIIT interspaced by one-minute interval of low-intensity exercise), completing 10 sets of HIIT with an overall exercise session time of 20 minutes. The intensity will be set at 85-90% PPO (from CPET) during high-intensity, (aiming to achieve 85-100% HRMax), and at 20-25%PPO during low-intensity bouts. The variation from high to low intensity will be achieved by altering the cycle cadence (rpm). This work to rest ratio has been selected as although HIIT is often prescribed in similar clinical populations using 4-minute intervals at 85-95%HRMax (33), a large RCT recently concluded that HIIT at this intensity is hardly feasible, at least not for a full 4-minutes (15). Our personal experience with cardiac patients has demonstrated that patients may exceed their peak heart rate (from CPET) during HIIT sessions. This is also likely to be the case for those with IC, especially those who are unable to achieve a maximal effort CPET. We will adopt a pragmatic approach to this by allowing it to occur but monitoring on a case-by-case basis and will reduce intensity when deemed appropriate. We will also record these occurrences to allow appropriate reporting.

The HIIT sessions will be preceded and followed by a 10-minute warm up and cool down as is standard practice in exercise rehabilitation for older adults with chronic disease. In addition, patients will be monitored for up to 10 minutes following the cool-down to ensure heart rate is returning to near resting values and/or any symptoms have subsided.

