The HIIT intervention will be performed by using a cycle ergometer with exercise prescription based on the workload achieved during a cycle CPET. The use of a treadmill may preclude patients from reaching their prescribed HIIT training zones due to the onset of claudication whilst a cycle may reduce the risk of falls in very deconditioned patients (34). It has been demonstrated that the limiting symptoms during treadmill walking were often experienced in the leg, mainly the calf, whereas the limiting symptoms during cycling were much more varied (34). Furthermore, one study, albeit small, noted that cycle testing was better tolerated than treadmill testing, which is important considering that the HIIT training zone requires the patient to exercise to near-maximal levels, similar to during a CPET (35).

Inclusion criteria:

- Community dwelling adults aged 18 or over.
- ABPI <0.9 at rest or a drop of more than 20mmHg after exercise testing
- Ability to walk unaided
- English speaking and able to comply with exercise instructions

Exclusion criteria:

- Patients who are unable to provide informed consent
- Critical limb ischaemia/rest pain
- Active cancer treatment
- Significant comorbidities precluding participation in exercise testing and/or training as per the American College of Sports Medicine Guidelines (19).
- Resting/uncontrolled tachycardia (>100bpm) and/or Resting/uncontrolled hypertension (SBP >180mmHg or DBP >100mmHg)
- Symptomatic hypotension

Additional exclusion criteria

Further to analysis of CPET results, patients will be prevented from continuing their involvement in the study if there is indication of:

- Exercise-induced ischaemia or significant haemodynamic compromise.

N.B. – Patients who are able to perform a maximal effort CPET according to previously published guidelines (19) will undergo the intervention which will be prescribed on the basis of their initial CPET. This will be referred to as maximal HIIT.

Patients unable to perform a maximal effort CPET, will still undergo the intervention which will be prescribed on the basis of their initial CPET values, but will be referred to as submaximal HIIT.

Subject recruitment

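### For patients with a submaximal baseline CPET, a heart rate inside the 85-100% range does not show that the primary tolerability outcome was met at high intensity

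*Combined protocol and SAP*

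**What the plan says.** Under *Primary outcomes measures*, the third primary component is "tolerability, assessed by patient ability to achieve and maintain exercise in the appropriate exercise intensity domain". The tolerability paragraph of *Primary endpoint – safety, utility and tolerability* makes this operational. Heart rate is collected throughout each session, and "this will then be compared to the 85-100%HRMax training range that has been prescribed". The same paragraph attaches a consequence: "If patients are not able to achieve 85-100%, this will determine the suitability of this HIIT protocol in this population". *Descriptive statistics and statistical analysis* repeats the comparison and names the source of the range: "tolerability will be assessed by comparing the mean heart rate achieved during each HIIT session to the 85-100% maximum heart rate range calculated from CPET".

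The *High intensity interval training (HIIT) programme* section takes the workload from the same test, at 85-90% of peak power output, with 85-100% of maximum heart rate as the aim. It also reports the team's experience that cardiac patients may exceed their CPET peak heart rate during HIIT, and adds: "This is also likely to be the case for those with IC, especially those who are unable to achieve a maximal effort CPET". Such occurrences are allowed, monitored case by case and recorded for reporting.

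The N.B. under *Additional exclusion criteria* deals with patients who do not reach maximal effort: "Patients unable to perform a maximal effort CPET, will still undergo the intervention which will be prescribed on the basis of their initial CPET" values. It gives them the separate label of submaximal HIIT. The statistical section plans a sub-group comparison of maximal with submaximal patients, without naming the outcomes it covers.

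**The concern.** The range that defines success is a percentage of each patient's own CPET peak. For a patient whose test was not maximal, that peak is the heart rate at which he or she stopped, and no other reference is given: no age-predicted value, repeat test or later update. The further the test falls short, the lower the range becomes. Two patients can both be scored as in range while working at quite different fractions of their true maximum.

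This matters because the question is whether patients with claudication can reach and hold a high intensity, and the protocol lets the answer decide whether this form of HIIT suits the population. The protocol sets a high standard for intensity. Its background calls an earlier study's 80% of maximum workload slightly conservative and puts usual HIIT at 85-95% of peak workload or heart rate. A tolerability result that cannot show whether that zone was reached leaves the suitability conclusion open for the patients concerned.

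**Working it through.** The plan states no expected rate, threshold or power for tolerability, so there is no figure of its own to reproduce. The check traces the denominator and then rescales the range.

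**1. Denominator.** The maximal-HIIT and submaximal-HIIT groups are both prescribed from the initial CPET (N.B. under *Additional exclusion criteria*). The tolerability range is calculated from CPET (statistical section). Maximum heart rate is never formally defined, but the CPET peak is the only reading these sections support. The HIIT programme section expects that peak to be exceeded, above all after a non-maximal test.

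**2. Rescaling.** Let f = CPET peak heart rate / true maximum heart rate. This is an assumption, since the documents give no value. Then:

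- floor of the range = 0.85 × f of true maximum; ceiling = 1.00 × f
- 85% of true maximum lies at 0.85 / f of the CPET peak
- share of the range's width below 85% of true maximum = (0.85 / f − 0.85) / 0.15, capped at 1

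| f (assumed) | Range as % of true maximum | Share of range width below 85% of true maximum |
|---|---|---|
| 1.00 | 85-100 | 0% |
| 0.95 | 80.8-95 | 30% |
| 0.90 | 76.5-90 | 63% |
| 0.85 | 72.3-85 | 100% |
| 0.80 | 68-80 | 100% |

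The last column describes the width of the range, not a proportion of patients.

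**3. In beats per minute.** Take a true maximum of 150 bpm (assumption). The 85% floor is 0.85 × 150 = 127.5 bpm. If the CPET stopped at 120 bpm (f = 0.80), the range becomes 0.85 × 120 = 102 to 120 bpm. Every in-range value is then 68-80% of the true maximum. At 127.5 bpm the patient is at 127.5 / 120 = 106% of CPET peak, which is above the range.

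**4. Effect on a pooled attainment rate.** Let s be the share of submaximal patients (assumption; not in the documents), a the proportion of them scored in range, and t the proportion truly at 85% of maximum or more. The shift is s × (a − t).

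- All scored in range, none truly there (a = 1, t = 0): +10 points at s = 10% (7 of 70), +20 at 20% (14 of 70), +30 at 30% (21 of 70).
- All scored in range, 30% truly there (a = 1, t = 0.3): +7, +14 and +21 points.
- All truly there but all above 100% of CPET peak and counted as outside the range (a = 0, t = 1): −10, −20 and −30 points.

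These are bounds and illustrations, not estimates. The sign depends on a and t, which the documents do not give.

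**5. A second downward pull.** The statistical section uses the session mean. Work and rest alternate minute by minute at 1:1. If the low-intensity minutes are included, a patient at 90% in the work minutes and 70% in the rest minutes (assumed) averages (90 + 70) / 2 = 80%, which is outside the range. The plan does not say which minutes enter the mean.

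**The case against.** Several points on the other side have force.

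- **Direction.** A reader might infer that pooling biases the result towards tolerable. The documents do not support this. The protocol expects submaximal patients to exceed their CPET peak, and a value above 100% falls outside the range. A session mean that includes low-intensity minutes would also lower the score. This objection stands.
- **Size.** A reader might infer that in-range exercise in this group is only moderate. The documents define no such category, and give neither the share of submaximal patients nor the shortfall in their heart rate. The maximal-effort criteria are cited, not listed, and failing them does not establish a large shortfall. The protocol also chose cycling partly because claudication might keep patients on a treadmill from reaching their training zone. At f = 0.95 the floor falls only from 85% to 80.8%. This objection stands too.
- **Safeguards.** The submaximal label, the recording of exceedances and the sub-group analysis already make separate reporting possible. That is true, but the sub-group analysis does not name tolerability, and comparing the groups would still use each patient's own CPET peak as the denominator.
- **Pooling.** The plan defines no single tolerability statistic, and its statement on including all participants is framed in terms of adherence. So a decisive pooled figure is not stated. Equally, nothing sets submaximal patients apart when the overall result is read.
- **Restricting the result.** It is tempting to base the conclusion on maximal-effort patients alone. That would select on exercise capacity and narrow the population whose suitability is in question, so it is not recommended.

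**Conclusion.** The concern holds as a limit on what the measure can show. For patients with a submaximal CPET, an in-range heart rate is compatible with less than 85% of true maximum: the floor is 80.8%, 76.5% or 68% for f = 0.95, 0.90 or 0.80. When f is below 0.85 the whole range lies under that level, and a patient who truly reaches it is scored above the range. Neither result, read alone, shows whether intensity was high.

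The structural part rests on the protocol's own text: admission, prescription and scoring from the same test, and the expectation that its peak will be exceeded. The size rests on assumed values of f and of the submaximal share. The net direction in a pooled result is not established. In a descriptive pilot cohort this does not threaten the design, but it should be settled before the tolerability result is used to judge suitability.

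**What to change.** Amend the tolerability paragraph under *Primary endpoint – safety, utility and tolerability* and the matching text in *Descriptive statistics and statistical analysis*:

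1. State that the maximum heart rate used for the range is the CPET peak, and that in a submaximal test it may be below the true maximum.
2. Report tolerability side by side for maximal-CPET and submaximal-CPET patients, as well as overall, and name tolerability as an outcome of the planned sub-group analysis.
3. Describe submaximal patients as meeting, exceeding or not meeting their prescribed range. Do not count an in-range result as evidence that high intensity was reached.
4. Add a sensitivity analysis that re-expresses heart rate for every patient as a percentage of the highest sustained, artefact-checked heart rate in any study CPET or HIIT session. Define sustained and the artefact check in advance, and note that this value may still understate the true maximum in someone limited by symptoms throughout.

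Enrolment, prescription and conduct of sessions do not change. The data are already collected, since heart rate is recorded throughout each session and a CPET is done at each study visit. The cost is smaller groups with less precise estimates, some extra analysis, and possibly a less favourable tolerability figure.
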